Drug use disorders commonly follow a history of experiencing high levels of early-life stress (ELS) (Repetti, Taylor et al. 2002, Dube, Felitti et al. 2003, McFarlane, Clark et al. 2005, Cohen, Paul et al. 2006), which have been linked with neural dysfunction (Cohen, Grieve et al. 2006, Seckfort, Paul et al. 2008, Baker, Williams et al. 2013, Philip, Sweet et al. 2013). HIV and high ELS have combined pathological effects on brain morphometry and neurocognitive function in HIV+ patients (Clark, Cohen et al. 2012). MA abuse and high ELS have some common effects, both involving upregulation of neuroinflammatory processes. High levels of ELS also are associated with increases in pro-inflammatory cytokines (Pollitt, Kaufman et al. 2007, Carpenter, Gawuga et al. 2010, Slopen, Lewis et al. 2010). These findings suggest that high ELS may exacerbate MA-related neuropathology in HIV+ patients and therefore we will explore potential effects of ELS on treatment outcomes as well as interactions with ibudilast treatment. As recent stress and/or trauma may confound any associations between ELS and neuroinflammation or cognition, we will assess recent stress and trauma using the Perceived Stress Scale (PSS-14) and the Posttraumatic Stress Disorder Checklist - Civilian (PCL-C) and control for these in our analyses.

Research Plan

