The study is a phase 2 clinical trial to determine the safety and efficacy of IBUD for the treatment of MA dependence. The trial will be performed at the UCLA outpatient research clinic in Hollywood, California. Treatment-seeking MA dependent volunteers will undergo screening and eligibility assessments, including determination of HIV serostatus, during a two-week placebo lead-in with a high value contingency management (CM) behavioral intervention aimed at assessing participants' ability to adhere to medication taking and initiate MA abstinence prior to the start of medication, both important predictors of subsequent treatment outcomes (Bisaga, Aharonovich et al. 2005, Anderson, Reid et al. 2009, Bisaga, Aharonovich et al. 2010). Eligible participants (N = 140) will be randomized, stratified by HIV serostatus, to IBUD (50 mg BID) or placebo (BID) treatment for 12 weeks, with twice weekly clinic visits for counseling, urine drug tests, and safety/medication adherence monitoring (Figure 4). An urn randomization procedure will be used to balance the following variables between active and placebo groups: MA use during the two-week placebo/CM lead-in period, gender, ethnicity (Hispanic versus not Hispanic), marijuana dependence, and baseline cognitive function.

Figure 4: Study Schema

The study is powered to detect a statistically significant benefit of IBUD over placebo on the primary study outcome, MA abstinence during the final two weeks of treatment (at least one of the two possible urine drug screens each week is available during weeks 11 and 12 and all available samples are MA negative, the FDA-preferred primary efficacy outcome for phase 2 stimulant trials) in the total sample (N = 140). Treatment retention for participants receiving IBUD versus placebo will also be compared.

Secondary analyses will examine medication tolerability and adverse events, as well as treatment outcomes in pre-specified subgroups defined by level of medication adherence, the ability to achieve initial MA abstinence during the placebo/CM lead-in, and baseline HIV serostatus. Exploratory analyses aimed at probing the mechanism of action for IBUD in MA dependence will examine potential associations between treatment outcomes/medication effects and a panel of inflammatory and neurotrophic markers as well as polymorphisms in dopaminergic and GDNF genes.

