Concomitant Medications: All subjects will be asked about concomitant medications weekly during the lead-in and outpatient treatment period. Concomitant medications include both OTC and prescribed medications.

Early Life Stress Questionnaire (ELSQ): The Early Life Stress Questionnaire (McFarlane, Clark et al. 2005) (ELSQ) is a self-report questionnaire that considers 19 adverse life events (crime, sexual abuse, family conflict, bullying, etc.). High ELS is defined as exposure to ≥ 3 ELS events prior to age 19 (Cohen, Paul et al. 2006, Paul, Henry et al. 2008, Seckfort, Paul et al. 2008, Clark, Cohen et al. 2012), consistent with the rates of ELS in the general population (Cohen, Paul et al. 2006). Previous studies (Cohen, Grieve et al. 2006, Cohen, Paul et al. 2006, Seckfort, Paul et al. 2008, Clark, Cohen et al. 2012) have shown that using a cut-point of ≥ 3 ELS events provides the greatest discrimination on the basis of ELS for behavioral and neural measures. The ELSQ will be administered during week 3.

Perceived Stress Scale (PSS-14): The PSS-14 is a validated, self-report questionnaire that assesses the extent to which individuals perceive their life to be stressful (Cohen and Williamson 1988). The PSS-14 will be administered during baseline.

Posttraumatic Stress Disorder Checklist - Civilian version (PLC-C): is the most commonly used self-report questionnaire assessing number and severity of PTSD symptoms. The PLC-C will be administered during week 3.

Genotyping/SNP: 10 ml whole blood will be collected at baseline for DNA extraction for genotyping analyses.

Hamilton Depression Rating Scale (HAMD) (Riskind, Beck et al. 1987): Completed in just 5 to 10 minutes, the HAMD can be used to quickly evaluate symptom severity, to confirm a diagnosis of depression, to explore depressive symptoms, and to measure treatment outcome. The HAMD will be administered during the lead-in period and weekly during the medication and follow-up phase.

HIV CD4 Count and Viral Load: Participants who are HIV+ will have CD4 count and viral load measured at baseline, at the termination of medication (week 13), and at the last follow-up visit (week 16).

HIV medication adherence: Participants who are HIV positive will have their HIV medication adherence assessed monthly by asking them to estimate the proportion of their medications that they took in the past month.

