During weeks 4 and 13, participants will repeat the following tasks: Montreal Cognitive Assessment; MATRICS CPT-II; HVLIT-R; BVMT-R; SST; TMT; DDT; WAIS-IV Letter Number Sequencing ; WAIS-IV Symbol Search, WAIS-IV Digit Symbol Coding; N-Back Task; DKEFS Color Word Interference and the Iowa Gambling Task.

Data Analysis: The primary objective of this study is to determine the efficacy of IBUD as a treatment for MA dependence and to provide FDA with sufficient data to advise whether IBUD should move forward for marketing as a MA dependence treatment. The primary outcome variable is the FDA-specified criterion of significant MA abstinence at the end of treatment defined as no self-reported MA use during the final two weeks of treatment (weeks 11/12) confirmed via urine drug screens (at least one of the two possible urine specimens each week is available during weeks 11 and 12 and all available urine specimens are MA-negative). The study is powered to detect a significant difference in the proportion of participants achieving this outcome in the IBUD versus placebo groups. Additional measures of clinically meaningful reductions in MA use during treatment will also be assessed in the event that IBUD produces effects on MA use that do not meet the abstinent at end of treatment threshold. In addition to MA use outcomes, treatment retention, an important clinical variable that is associated with long-term treatment outcomes in substance abuse treatment (Hser, Evans et al. 2004), with IBUD versus placebo will be compared. Effects of potential confounders on each of these outcomes will also be examined including: (1) medication non-adherence, (2) medication safety and tolerability (adverse event rates), and (3) ability to achieve initial MA abstinence with the CM intervention during the two week lead-in period.

A general univariate strategy will be used to test for differences between conditions at baseline and along all outcome variables using bivariate analyses (i.e., t-tests/ANOVA for continuous variables; χ^2 for dichotomous variables). A multivariate analysis will also be used when appropriate to control for co-variables known to influence MA dependence treatment outcomes including age, gender, baseline severity of MA dependence, HIV status, and ability to achieve initial abstinence during the CM lead-in.

Aim 1: To determine whether IBUD reduces MA use more than placebo among MA dependent participants.

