Examination of potential confounders Rates of adverse events and medication adherence in the IBUD and placebo groups will be calculated and compared. Medication adherence will be assessed as a continuous variable: the proportion of twice-weekly urine drug samples positive for riboflavin (≥ 900 ng/ml riboflavin as determined via quantitative fluorimetry), and as a dichotomous variable: medication adherent ($\geq 80\%$ of twice-weekly urine drug screens positive for riboflavin). Adherence will also be assessed via qualitative measurement of IBUD and metabolites in urine and serum samples, which is the gold standard for assessing adherence in the IBUD group but is limited by the fact that assessment of adherence in the placebo group is not possible. Models for MA use outcomes will be repeated including the continuous measure of adherence as a co-variate. The models will also be run with the sample stratified as medication adherent versus non-adherent. As pre-treatment abstinence is an important predictor of treatment outcomes and medication response in stimulant dependence trials (Elkashef, Rawson et al. 2008, Bisaga, Aharonovich et al. 2010), the sample will be stratified by ability to achieve initial abstinence with CM during the two-week lead-in period to explore whether medication effects may differ in these subgroups.

Aim 2: To determine whether IBUD results in longer treatment retention than placebo among MA dependent participants.

Hypothesis 2: IBUD will result in significantly greater treatment retention than placebo

Analysis: The mean number of days retained, defined as the number of days from the start of study medication to the final clinic visit during the 12 week treatment period, will be compared for IBUD versus placebo via t-test. Cox proportional hazards model will be used to compare days retained for IBUD versus placebo controlling for co-variables including age, gender, and baseline MA use. These analyses will then be repeated with the sample stratified by ability to achieve initial abstinence with CM during the two-week lead-in period to explore whether medication effects may differ in these subgroups.

The following exploratory HIV-related aims will be address in the HIV positive participants.

Aim 3: To determine whether IBUD improves biological (CD4 count; HIV RNA) and neurocognitive outcomes more than placebo among HIV-positive MA dependent participants.

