Hypothesis 3: IBUD will result in greater improvements in CD4 count, HIV viral load, and neurocognitive functioning than placebo among HIV positive participants.

Analysis: Change scores for CD4 count, HIV viral load, and scores on neurocognitive assessments will be calculated between baseline and end of medication treatment. The mean change score for each measure will be calculated for IBUD versus placebo. A linear regression model will be used to assess the mean change in measures for IBUD versus placebo after controlling for possible confounders such as gender, MA abstinence during the two-week lead-in period, and medication adherence.

Aim 4: To determine whether IBUD improves behavioral outcomes (sexual transmission behaviors; uptake and/or adherence to HIV medications) relative to placebo among HIV-positive MA dependent participants.

Hypothesis 4: IBUD will result in greater reductions in HIV risk behaviors and increased HIV medication uptake/adherence than placebo among HIV positive participants.

Analysis: The proportion of participants reporting HIV sexual risk behaviors in the IBUD and placebo groups will be calculated. The proportion of participants reporting receipt of HIV medications as well as the proportion of medication they report taking will be calculated. The mean number of self-reported HIV

[figure not shown]
sexual risk behaviors for IBUD versus placebo will be compared via t tests and then in a linear regression model controlling for potential confounders. The mean HIV medication adherence rate (proportion of medication taken) for IBUD and placebo will also be compared via t test and then linear regression model.

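### Adherence measured during treatment is used as a confounder in the repeated Aim 1 models and the Aim 3 regression, where it can create an apparent drug effect; the primary intention-to-treat comparison is unaffected

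*Combined protocol and SAP*

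**What the plan says.** All references are to the combined protocol and SAP.

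- **Data Analysis, opening paragraph.** After the Aim 1 and Aim 2 outcomes: "Effects of potential confounders on each of these outcomes will also be examined including: (1) medication non-adherence".
- **Examination of potential confounders (Aim 1).** Adherence is "the proportion of twice-weekly urine drug samples positive for riboflavin", and is dichotomised at 80% or more of samples positive. Then: "Models for MA use outcomes will be repeated including the continuous measure of adherence as a co-variate". Next: "The models will also be run with the sample stratified as medication adherent versus non-adherent".
- **Research Plan.** The secondary analyses include outcomes in "pre-specified subgroups defined by level of medication adherence".
- **Aim 3, Analysis.** For CD4 count, viral load and neurocognitive change scores, the one regression described compares the arms after "controlling for possible confounders such as gender, MA abstinence during the two-week lead-in period, and medication adherence".
- **Aim 1, Analysis.** The primary logistic model is intention to treat. It lists age, gender, baseline MA-use days and HIV status, but not adherence.
- **Background and Study Measures.** Recent stress and trauma scales, including the PTSD checklist, are to be measured so as to "control for these in our analyses". "The PLC-C will be administered during week 3", that is, during treatment.

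**The concern.** A confounder of a drug-versus-placebo comparison would have to be a cause of assignment, or share a cause with it. Randomisation rules that out for anything measured afterwards. On-treatment adherence can instead be a result of assignment: Medication Adherence Support/Monitoring names side effects as a barrier to taking the capsules. It can also share causes with outcome: the Research Plan describes ability to adhere and ability to start abstinence in the lead-in as important predictors of later results.

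When both hold, comparing arms at equal adherence compares unlike people. If IBUD is harder to tolerate, those who still reach 80% on IBUD are on average a better-prognosis group than those who reach it on placebo. So are those who fall below 80%, because some people with good prognosis have moved down. Both strata then favour IBUD, although the drug does nothing.

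The practical stake is a null primary result followed by a claim of benefit in adherent patients, drawn from an analysis that the plan has already pre-specified.

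**Working it through.** **Plan's own figure.** There is none to reproduce. The documents give no expected adherence by arm and no estimate of this bias, and the sample size does not depend on it. All inputs below are assumptions, except 70 per arm, 24 scheduled samples (2 × 12 weeks), the 80% cut and the one-sided 0.05 level.

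**Step 1: bias from stratifying, no drug effect.** Let U ~ N(0,1) be a shared prognostic factor and T = 1 for IBUD.

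- logit P(abstinent) = −1.2 + U, with no T term
- logit P(adherent) = 0.4 + U − b·T
- P(abstinent | adherent, T) = E[P(abstinent | U)·P(adherent | U, T)] / E[P(adherent | U, T)], and likewise for non-adherent

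Averaging over U numerically gives 27% abstinent overall in both arms. Odds ratios are computed before the percentages are rounded.

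| b | Adherent, placebo / IBUD | Abstinent among adherent, placebo / IBUD | OR | Abstinent among non-adherent, placebo / IBUD | OR |
|---|---|---|---|---|---|
| 0 | 58% / 58% | 32.6% / 32.6% | 1.00 | 19.0% / 19.0% | 1.00 |
| 0.5 | 58% / 48% | 32.6% / 34.2% | 1.07 | 19.0% / 20.2% | 1.08 |
| 1.0 | 58% / 38% | 32.6% / 35.9% | 1.16 | 19.0% / 21.4% | 1.17 |
| 1.5 | 58% / 29% | 32.6% / 37.6% | 1.25 | 19.0% / 22.6% | 1.25 |

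Example, b = 1.0, adherent: (0.359/0.641) / (0.326/0.674) = 0.560/0.484 = 1.16. Simulations of 4 million subjects agree to about 0.01. If IBUD raised adherence instead, swapping the arms inverts the ratios (1/1.07 = 0.93), so the bias would run against IBUD.

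**Step 2: the covariate model at trial size.** Simulated trials of 70 per arm, adherence from 24 samples, no drug effect, abstinence 13% to 30%, and a trait effect on abstinence of 0.5 to 1.5 log-odds per SD. There were 1,000 trials per setting for type I error and 400,000 participants per setting for odds ratios.

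| Mean adherence, placebo / IBUD | OR adjusted for adherence | One-sided type I error | OR in ≥80% stratum | One-sided type I error |
|---|---|---|---|---|
| 0.69 / 0.69 | 1.00–1.02 | 4.3–5.7% | 0.99–1.02 | 4.3–5.7% |
| 0.69 / 0.60 | 1.14–1.38 | 7.7–19.2% | 1.11–1.28 | 4.8–10.4% |
| 0.69 / 0.50 | 1.29–1.95 | 12.3–47% | 1.24–1.68 | 7.0–20% |
| 0.69 / 0.40 (extreme) | 1.49–2.91 | 15.6–74% | 1.34–2.34 | 10.1–23% |

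With adherence left out, the odds ratio was 0.99–1.02 and type I error 3.8–6.9%. The Monte Carlo standard error is √(0.05 × 0.95/1000) = 0.7 percentage points.

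**Step 3: Aim 3.** In a linear model, adjusted difference = unadjusted difference − δβ. Here δ is the effect of IBUD on adherence and β the within-arm slope of the change score on adherence. If IBUD lowers adherence (δ < 0) and β reflects only shared prognosis with β > 0, the adjusted difference shifts towards IBUD by |δ|β with no true effect.

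**Step 4: the denominator.** The plan does not say whether adherence is a share of samples given or of samples scheduled. Someone who leaves after week 4 with every urine positive scores 8/8 = 100% on the first reading and 8/24 = 33% on the second, and so changes stratum. Under Study Medication Stopping Rules, adherence checks end when medication is discontinued and urine for fluorimetry is collected for at most one more week. Which samples exist can therefore itself depend on tolerability.

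**The case against.** - **Scope.** A reader might infer that the randomised comparison as a whole is broken. The documents do not support that. The primary model is intention to treat and lists only baseline covariates, the Aim 2 Cox model does not list adherence, the Aim 1 adherence models are repeats, and the adherence subgroups are labelled secondary. This stands in full.
- **Aim 3 is exploratory and unpowered.** Mean change by arm is also calculated, and the general strategy in Data Analysis provides bivariate tests on all outcomes. An unadjusted comparison therefore exists. This lowers the stakes, but does not justify an adherence term in the only regression described.
- **PTSD checklist.** A reader might infer that a week-3 measure is being adjusted for in drug-versus-placebo models. Background gives a narrower purpose: to handle confounding of early-life-stress associations with neuroinflammation or cognition, which is an observational question. No stated arm comparison contains the checklist. The opening left is the early-life-stress-by-ibudilast interaction work, where the text is silent. The early-life stress questionnaire asks about events before age 19, so giving it at week 3 does not make that exposure post-randomisation.
- **Missed urines.** It is tempting to say that every missed specimen lowers adherence and also counts as failure. The primary outcome needs only one of two specimens in each of weeks 11 and 12, and drop-outs are to be followed weekly for urine. A missed sample is not in itself a failure.
- **Size.** The adherence differences and trait effects are assumed. Exclusion at lead-in for more than one low riboflavin sample, adherence counselling, and phase I adverse events described as similar on drug and placebo may all keep the arms close. If they do, the bias disappears. That is a fair limit on magnitude; the plan does not ensure it.

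**Conclusion.** The point holds for the secondary and exploratory models and no further. The plan treats a post-randomisation variable as a confounder, and under plausible conditions the resulting estimates do not measure a drug effect. With no true effect, the assumed inputs give within-stratum odds ratios of about 1.07 to 1.25. Adjusting for continuous adherence gives 1.14 to 1.95 for mean adherence gaps of 0.09 to 0.19, and more in the extreme case. Two assumptions carry this: IBUD changes adherence, and an unmeasured factor drives both adherence and outcome. Without the first, there is no bias. These figures show what the models can do; they do not predict this trial. Primary-outcome inference and sample size are unchanged. The change should be made because it costs little and removes an easily misquoted analysis.

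**What to change.** 1. **Aim 3.** Drop adherence from the regression and keep baseline covariates only.
2. **Aim 1.** Replace the adherence-adjusted and adherence-stratified arm comparisons with a complier-average (instrumental-variable) analysis, with randomisation as the instrument: (abstinence on IBUD − abstinence on placebo) / proportion of the IBUD arm counted as having taken the drug. Exposure is needed in the IBUD arm only, so the plan's remark that drug levels cannot assess placebo adherence is no obstacle. Urine aliquots are stored twice weekly, and IBUD is not clinically available in the US, so placebo crossover is unlikely.
3. **Define taken in advance.** An 80% cut would class partial takers as unexposed and break the exclusion assumption. Any-exposure would count nearly everyone, since the first dose is observed. The share of scheduled samples with drug or metabolite detected is an alternative, at the price of assuming a linear effect. State how missing samples count.
4. **If the planned adherence models are kept,** label them descriptive and non-causal, and use scheduled samples as the denominator. Adherence rates by arm are already to be reported.
5. **PTSD checklist.** State that it stays out of any drug-versus-placebo or early-life-stress-by-ibudilast model. Its timing need not move: 85 participants were already randomised when this version was written, and a move would mix timings.

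The cost is SAP wording. The complier-average interval is wider, by roughly 1/0.48 = 2.1 times on the risk-difference scale if 48% count as takers. It also rests on assignment acting only through taking the drug. It gives essentially the same test as intention to treat, so it cannot rescue a null primary result.

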Comprehensive feedback will be provided to subjects who are judged not suitable for the study for any psychiatric or medical reason. Participants who fail to complete all baseline data collection and procedures within two weeks will not be randomized into the trial. Subjects who are MA abstinent upon entry to the lead-in period are excluded as they are highly likely to remain abstinent regardless of treatment (Hillhouse, Marinelli-Casey et al. 2007).

Randomization Procedures: When participants are determined to be eligible and are cleared by the study physician for participation, they will be randomized to either IBUD 50 mg BID or placebo BID, stratified by baseline HIV serostatus (up to 70 HIV positive). In addition, within each strata an urn randomization procedure (Stout, Wirtz et al. 1994) will be used to provide multivariate balance across conditions along the following variables that may influence treatment outcomes: MA abstinent versus not abstinent as confirmed via urine drug screen during the second week of the lead-in period, (MA abstinence will be confirmed with at least two urine drug screens negative for presence of MA and no urine drug screen positive for MA, while all other urine drug screen results will be considered not abstinent), gender (biologic male versus female), ethnicity (Hispanic versus not Hispanic, marijuana dependence (dependent versus not as assessed by SCID), and baseline cognitive function (greater than 26 on the MoCA versus 25 or less). Participants will be considered to have entered the trial for the intention to treat analysis at the point of randomization. The randomization key will be maintained off-site in the Research office.

Outpatient Treatment Procedures: Participants will attend the outpatient research clinic twice weekly for urine drug screens, counseling, assessment of substance use and other standardized research measures (see below), and safety and medication adherence monitoring for 12 weeks of treatment. During this time repeat safety labs and a repeat EKG will be conducted at weeks 3 and 8. At week 13, a termination assessment will consist of a repeat physical, EKG, safety labs, and other behavioral assessments and cognitive testing, followed by a final brief health check 30 days later for post-medication safety monitoring.

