"Drop-out" Subject Tracking: Subjects who have not rescinded consent, but are no longer available/interested in attending twice-weekly visits ("drop-outs") will be followed using alternative methods. Every effort will be made for all subjects in the trial to attend a minimum of one clinic visit a week. However, attrition in Phase 2 trials tends to be high. In order to comprehend the reasons for dropping out of the clinical trial, we will arrange to meet the research subject weekly during the course of the medication phase of the trial at a mutually-agreeable location and/or taxi the participant to the clinic to collect a urine drug sample and complete data typically collected on a weekly basis.

Termination and Follow-Up Procedures: Once participants complete the 12-week medication period, they will be asked to return during week 13 for a repeat EKG, labs, and physical exam, and for follow-up assessment. On the final visit (approximately 30 days after completing study medications), participants will complete a brief health check with a study clinician. Every effort will be made to retain all participants through the entire trial. Our group has developed effective procedures for retaining individuals in controlled experimental drug trials (e.g., building strong relationships with study participants, telephone, texting, and letter procedures). Similar strategies will be implemented for this proposed study. However, we recognize that not all participants will complete the trial. Early termination criteria by the principal investigator are defined as two consecutive weeks (or four consecutive visits) of missed study activity or data collection visits. Participants who end the trial early, for whatever reason, will be asked to attend the 4-week follow-up visits.

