Twice-weekly clinic attendance during weeks 11-12 (\$25/visit x 4 visits)	\$100
Iowa Gambling (Half of the participants (n = 70) will receive compensation) task at baseline and weeks 4 and 13 (\$10 per completed task)	\$30
Connors' CPT task at weeks 2, 6, and 10 (\$5/completed task x 3 tasks)	\$15
Cognitive battery at week 4 and termination (\$20/battery x 2)	\$40
Weekly clinic attendance during weeks 13, 14 and 15 (\$10/visit)	\$30

Completion of study close-out visit (week 16)	\$15
Total possible earned by participant	\$565 or \$595

Potential Participant reimbursement without neurocognitive testing (post- July 2016)

Activity	Amount
CM intervention during lead-in (\$15 for the first MA-free urine, \$25 for second, and \$40 for third)	\$80
Completion of screening measures	\$25
Completion of Medication adherence check (\$5/week x 12 weeks)	\$60
Twice-weekly clinic attendance during weeks 1-10 (\$10/visit x 20 visits)	\$200
Twice-weekly clinic attendance during weeks 11-12 (\$25/visit x 4 visits)	\$100
Weekly clinic attendance during weeks 13, 14 and 15 (\$10/visit)	\$30
Completion of study close-out visit (week 16)	\$15
Total possible earned by participant	\$510

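### Aim 2 dates retention by the last clinic visit without separating treatment visits from drop-out tracking visits, so tracking carried out at the clinic biases the retention comparison

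*Combined protocol and SAP*

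**What the plan says.** In the combined protocol and SAP, the Data Analysis section (Aim 2, Hypothesis 2) takes days retained as the outcome, "defined as the number of days from the start of study medication to the final clinic visit during the 12 week treatment period". The means "will be compared for IBUD versus placebo via t-test", and a "Cox proportional hazards model will be used to compare days retained for IBUD versus placebo", adjusted for covariates. Neither analysis restricts the type of visit or mentions gaps in attendance.

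The Drop-out Subject Tracking section covers people who are "no longer available/interested in attending twice-weekly visits". It is limited to "Subjects who have not rescinded consent". Staff will arrange to see them weekly during the medication phase, "at a mutually-agreeable location and/or taxi the participant to the clinic to collect a urine drug sample" and to complete the usual weekly data. The stated purpose is to learn why people leave. The section expects high attrition but gives no rate.

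Termination and Follow-Up Procedures sets an early-termination criterion: two weeks running, or four visits in a row, of missed study activity or data collection. The Aim 2 definition does not refer to it.

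Under Aim 1, the Joint Probability Index multiplies the probability of being retained by the probability of being abstinent. It does not define retained.

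**The concern.** The tracking window and the retention window are the same 12 weeks. A visit made because someone has left regular treatment therefore qualifies, on the words of the definition, as that person's final clinic visit. Two things follow.

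- The score depends on where staff meet the person. Take two people who stop attending at the end of week 3 (day 21). One is taxied in weekly through week 12 and scores about 12 × 7 = 84 days. The other is met off-site and scores about 21.
- The arm with more drop-outs has more people whose score can be raised. If tracking works equally well in both arms, that arm gains more days and the difference shrinks.

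Retention is the second efficacy hypothesis and, unlike Aims 3 and 4, is not labelled exploratory. The t-test and the Cox model both use this variable, and the Joint Probability Index may inherit it.

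**Working it through.** **Reading the sections together.** No section says how tracking contacts enter the retention variable. The early-termination criterion does not fill the gap. Aim 2 does not invoke it, and a tracked person who supplies weekly data may never meet it, because it counts missed data collection.

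**Plan's own figure.** There is none to reproduce. The Power calculations section covers only the abstinence outcome. For Aim 2 the documents state no effect size, alpha, sidedness or drop-out rate.

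**Inputs.** From the documents: 70 per arm and 12 weeks (84 days). Assumed: two-sided alpha of 0.05; drop-out proportion d; drop-out days uniform on 0–80 (mean L = 40, variance 80²/12 = 533.3); completers' last visit on days 80–84 (mean C = 82, variance 1.33); a share f of drop-outs whose last clinic visit becomes a tracking visit on days 78–84 (mean T = 81, variance 3).

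**Means.** For each arm, mean = (1 − d)C + d[(1 − f)L + fT]. With the same f in both arms:

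difference = (d_placebo − d_ibudilast) × [C − L − f(T − L)] = (d_placebo − d_ibudilast) × [42 − 41f].

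If tracked drop-outs are dated like completers (T = C), this is exactly (1 − f) times the true difference. As T moves back towards L, the shrinkage disappears.

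**Power.** SE = √[(variance_placebo + variance_ibudilast)/70] and power ≈ Φ(difference/SE − 1.96). For 50% v 25% drop-out and f = 0:

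- Placebo variance = 0.5(40² + 533.3) + 0.5(82² + 1.33) − 61² = 708.3.
- Ibudilast variance = 0.25(40² + 533.3) + 0.75(82² + 1.33) − 71.5² = 465.1.
- SE = √(1173.4/70) = 4.09.
- Power ≈ Φ(10.5/4.09 − 1.96) ≈ 0.73.

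The other rows follow in the same way, with the tracked group (mean 81, variance 3) as a third component.

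| Drop-out, placebo v ibudilast | f | Mean days, placebo | Mean days, ibudilast | Difference | SE | Power |
|---|---|---|---|---|---|---|
| 50% v 25% | 0 | 61.0 | 71.5 | 10.5 | 4.09 | 73% |
| 50% v 25% | 50% | 71.3 | 76.6 | 5.4 | 3.21 | 39% |
| 50% v 25% | 75% | 76.4 | 79.2 | 2.8 | 2.38 | 22% |
| 40% v 20% | 0 | 65.2 | 73.6 | 8.4 | 3.83 | 59% |
| 40% v 20% | 50% | 73.4 | 77.7 | 4.3 | 2.93 | 31% |
| 40% v 20% | 75% | 77.5 | 79.8 | 2.3 | 2.15 | 18% |

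Simulations of 4,000 trials per setting agree to within about one percentage point of power.

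**A different drop-out pattern.** A second simulation used exponential drop-out, week-12 retention of 50% v 70%, and tracked drop-outs dated to day 84:

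| f | Difference, days | Power |
|---|---|---|
| 0 | 10.2 | 61% |
| 25% | 7.5 | 43% |
| 50% | 5.0 | 28% |
| 75% | 2.5 | 16% |
| 90% | 1.0 | 6% |
| 100% | 0 | – |

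**Unequal tracking.** Let true drop-out be 50% in both arms, with 25% of placebo and 50% of ibudilast drop-outs brought in late.

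- Placebo mean = 0.375 × 40 + 0.125 × 81 + 0.5 × 82 = 66.1.
- Ibudilast mean = 0.25 × 40 + 0.25 × 81 + 0.5 × 82 = 71.3.
- The result is a spurious 5.1 days favouring ibudilast, with SE 3.91, significant in about 26% of trials. Under exponential drop-out it is 5.9 days and about 28%.

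All power figures are for the t-test. No separate calculation was made for the Cox model.

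**The case against.** The strongest reply is that this is one ambiguous definition and that its effect is unknown. Much of that is fair.

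- A reader might infer that successful tracking erases the retention difference, or that the problem arises whenever tracking goes to plan. The documents do not support either. Off-site contacts add no clinic visit, people who rescind consent are not tracked, and the split between venues is not given. The difference vanishes only if essentially every drop-out is brought to the clinic through week 12.
- The pull towards zero requires similar in-clinic tracking in both arms. This stands as a condition on the direction.
- Dating every tracked drop-out to the last week is the most damaging timing. Tracking that fades earlier dilutes less. This also stands.
- Someone in tracking has not necessarily left treatment. The protocol also aims for at least one clinic visit a week, and a once-weekly attender may still be taking medication and receiving counselling. Entry into tracking is not a dated event either. This rules out a fix that simply ends retention when tracking begins.
- Three related points carry little weight. The higher payment for "Twice-weekly clinic attendance during weeks 11-12" applies to both arms, and nothing says tracked drop-outs receive it. Oral kits used while away cost at most the days since the last clinic visit. The clock starts at first dose although "Participants will be considered to have entered the trial for the intention to treat analysis at the point of randomization", but the first dose is observed at the clinic after randomisation, and no frequency of never-dosed participants is given.

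The scoring rule itself is not answered by any of this. Followed as written, it credits in-clinic tracking visits as retention, and no other section corrects it.

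**Conclusion.** The concern holds in a conditional form. The Aim 2 definition counts an in-clinic tracking visit as retention, so the score depends on where a drop-out is met.

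With a similar in-clinic tracked share f in both arms, and contact lasting through week 12, the observed difference is about (1 − f) of the true one. At 50% v 25% drop-out and f = 50%, that means about 10.5 days falling to 5.4, and power about 73% falling to 39%. Unequal tracking can instead produce a difference where none exists.

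These figures show how the mechanism works and are not an estimate for this trial. Drop-out rates, f, timing and the alpha for Aim 2 are all assumed. Nor should the point be read as touching the primary abstinence outcome or its power calculation, neither of which uses the retention variable.

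**What to change.** In the Aim 2 analysis, define the end of retention as the last scheduled treatment visit attended at the clinic that meets two conditions:

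- it was not arranged under the drop-out tracking procedure;
- it came before any gap meeting the protocol's existing criterion of two consecutive weeks or four consecutive visits missed, with tracking contacts not counted as attendance.

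Record visit type at every contact, so that a participant who still comes to scheduled visits once a week is not scored as lost. Use tracking contacts, at the clinic or elsewhere, for methamphetamine-use outcomes only. Apply the same meaning of retained to the t-test, the Cox model and the Joint Probability Index. Settle this before unblinding.

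The cost is a visit-type flag, one revised definition, and lower reported retention in both arms. How much lower depends on how many drop-outs are tracked at the clinic. In the 50% v 25% example with f = 50%, the placebo mean would be 61.0 instead of 71.3 days and the ibudilast mean 71.5 instead of 76.6. No trial procedure changes beyond labelling the visits.
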